6.1.2 Calculation or derivation of pharmacodynamic variables

Not applicable

6.1.3 Calculation or derivation of pharmacokinetics

C_{\max} and t_{\max} for each volunteer will be determined by inspection of the plasma concentration-time profile. The λ_z will be calculated by log-linear regression of the terminal portion of the concentration-time profiles where there are sufficient data (a minimum of 3 plasma concentration values in the terminal log-linear phase, spanning an interval of at least 2 half-lives.) Terminal elimination half-life ($t_{1/2, \lambda_z}$) will be calculated as $0.693/\lambda_z$. The $AUC_{(0-t)}$ will be calculated by the linear trapezoidal rule ($AUC = AUC_{(0-t)} + C_{\text{last}}/\lambda_z$). $AUC_{(0-t)}$ will be extrapolated to infinity using λ_z to obtain AUC where there are sufficient data. Following the single dose administration of rosuvastatin, atorvastatin and simvastatin, the CL/F will be calculated as Dose/AUC.

6.2 Safety evaluation

6.2.1 Calculation or derivation of safety variables

Safety and tolerability will be assessed by the incidence and severity of AEs, clinical laboratory parameters (hematology, clinical chemistry, urinalysis), vital signs measurements, and physical examination findings.

Where standard summary statistics are referenced below, this will include the mean, standard deviation, median, minimum and maximum for continuous variables, and counts and percentages for discrete variables.

6.2.1.1 Adverse events

Adverse events will be summarized by System Organ Class and Preferred Term, using medical dictionary for regulatory activities (MedDRA). All adverse event data will be listed for all volunteers. Separate listings of all serious adverse events, deaths or other significant adverse events will be presented.

Safety data will be summarized and listed by study medications and ethnic groups.

6.2.1.2 Laboratory data

All laboratory safety data, incorporating hematology, clinical chemistry, and urinalysis data will be listed, with deviations from the normal range explicitly noted on the listings.

Continuous laboratory data will be summarized using standard summary statistics. Both absolute values and change from pre-dose baseline will be summarized.

Discrete laboratory data will be summarized using standard summary statistics.

6.2.1.3 Vital signs

Vital signs data will be summarized and listed using standard summary statistics. Both absolute values and change from pre-dose baseline will be summarized. In addition, mean plots showing change within treatment group across time will be produced for absolute values.

6.2.1.4 Physical examination

Physical examination abnormalities will be listed.

6.3 Genetics as a co-variate

Not applicable

6.4 Statistical methods and determination of sample size

6.4.1 Statistical evaluation

A comprehensive Statistical Analysis Plan (SAP) will be prepared and finalized before database lock.

6.4.2 Description of variables in relation to hypotheses

The primary question is whether the magnitude of the ethnic effect (Chinese or Japanese vs Caucasian) is equivalent when atorvastatin is compared to rosuvastatin or when simvastatin is compared to rosuvastatin. The test statistics are the ratios of the primary parameter ratios. For AUC, for example, the ratios are:

- $\frac{[AUC(\text{Chinese})/AUC(\text{Caucasian})]_{\text{Atorvastatin}}}{[AUC(\text{Chinese})/AUC(\text{Caucasian})]_{\text{Rosuvastatin}}}$
- $\frac{[AUC(\text{Japanese})/AUC(\text{Caucasian})]_{\text{Atorvastatin}}}{[AUC(\text{Japanese})/AUC(\text{Caucasian})]_{\text{Rosuvastatin}}}$
- $\frac{[AUC(\text{Chinese})/AUC(\text{Caucasian})]_{\text{Simvastatin}}}{[AUC(\text{Chinese})/AUC(\text{Caucasian})]_{\text{Rosuvastatin}}}$
- $\frac{[AUC(\text{Japanese})/AUC(\text{Caucasian})]_{\text{Simvastatin}}}{[AUC(\text{Japanese})/AUC(\text{Caucasian})]_{\text{Rosuvastatin}}}$

Ratios of C_{\max} ratios and $AUC_{(0-t)}$ ratios will also be examined.

6.4.3 Description of analysis sets

Statistical analyses for pharmacokinetic parameters will be performed on the evaluable population. A volunteer is considered evaluable if the volunteer satisfied the inclusion and exclusion criteria, completed the study, and had no major protocol deviation or violation.

All volunteers who received at least one dose of study medication will be included in the safety analysis.

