Clinical Pharmacology Study Protocol

Drug Substance Rosuvastatin calcium

Study Code D3560C00004

Date

A phase I, randomized, open label, single dose, 3-way crossover pharmacokinetic study comparing plasma exposure of rosuvastatin calcium, atorvastatin calcium, and simvastatin in healthy Chinese, Japanese, and Caucasian volunteers.

Sponsor:

The following Amendment(s) and Administrative Changes have been made to this protocol since the date of preparation:

Amendment No.	Date of Amendment
_____	_____
_____	_____
Administrative Change No.	Date of Administrative Change
_____	_____
_____	_____

This submission /document contains trade secrets and confidential commercial information, disclosure of which is prohibited without providing advance notice to AstraZeneca and opportunity to object.

ASTRAZENECA PROCEDURES IN CASE OF EMERGENCY, OVERDOSE OR PREGNANCY

In the case of a medical emergency you may contact the Study Delivery Team Leader. If the Study Delivery Team Leader is not available, contact the Study Delivery Team Physician at the AstraZeneca Research and Development site shown below.

Role in the study	Name	Address and Telephone number
Study Delivery Team Leader	Senior Study Delivery Operations Specialist	
Study Delivery Team Physician	Executive Director Clinical Pharmacology	
Drug Safety Physician	Senior Medical Director Drug Safety	

For further clarifications regarding:

- Procedures in case of medical emergency see Section [8.2](#)
- Procedures in case of pregnancy see Section [8.3](#)

PROTOCOL SYNOPSIS

A phase I, randomized, open label, single dose, 3-way crossover pharmacokinetic study comparing plasma exposure of rosuvastatin calcium, atorvastatin calcium, and simvastatin in healthy Chinese, Japanese, and Caucasian volunteers.

Investigator

Study centre(s), type and number of subjects planned

This will be a single center study conducted in the United States. Approximately 90 Healthy Chinese, Japanese, and Caucasian volunteers will be recruited to obtain at least 27 evaluable volunteers for each ethnic group. An evaluable volunteer is defined as a volunteer completing all study procedures from the screening period to the final blood sampling of the final crossover period.

Study period

Estimated date of first subject enrolled

Estimated date of last subject completed

Phase of development

I

Objectives

The primary objective of this study is to:

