3.3.5.3 Procedures for handling incorrectly enrolled volunteers

Volunteers not meeting the inclusion/exclusion criteria for this study should, under no circumstances, be enrolled. Volunteers not meeting the study criteria that are enrolled in error, incorrectly randomized, or if volunteers subsequently fail to meet the criteria for the study post enrollment, will be discontinued from the study. Volunteers discontinued due to these factors will undergo safety assessments before discontinuation and any adverse events will be recorded. These volunteers, if any, will be included for the safety analysis, but will not be included as evaluable volunteers in the analysis of the study.

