3.4.4 Concomitant medication

During the screening, in-patient, and washout periods, volunteers will be instructed that no additional medication will be allowed without the prior consent of the investigator. Prescription medicines are not allowed during this study at any time. All medications (OTC

products, dietary supplements, and herbal remedies) will be discontinued 1 week prior to entry into the CRC.

Study personnel will inquire if any concomitant medications were used during the washout periods upon readmission to subsequent Treatment Periods. Use of prescription medication is an exclusion criterion and volunteers will be discontinued if use of prescription medication has occurred during any restricted timeframe (1 week prior to CRC entry, in-patient periods, and washout periods). Any concomitant medications must be recorded on the appropriate CRF.

Any medication, which is considered necessary for the volunteer's safety and well-being, may be given at the discretion of the investigator(s). The administration of all medication (including investigational products) must be recorded in the appropriate sections of the case report form (CRF).

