6.4.4 Methods of statistical analyses

All demographic and baseline data, including medications, will be listed and summarized using standard summary statistics for continuous variables and frequency counts and percentages for categorical variables.

Pharmacokinetic data, C_{\max} , $AUC_{(0-t)}$, and AUC, $t_{1/2z}$, λ_z and CL/F, of each study medication will be summarized for each ethnic group using descriptive statistics, including geometric means and coefficient of variation, and listed. In addition, 95% confidence intervals (CI) for the mean pharmacokinetic parameters will also be presented. Time to peak plasma concentration, t_{\max} , will be summarized using the median value and range for each ethnic group.

Log-transformed C_{\max} , $AUC_{(0-t)}$, and AUC will be analyzed using a mixed model with the fixed effect of ethnicity, sequence, treatment, and period and random effect subject. Appropriate contrasts and their 90% CIs will be produced from the model, these estimates will then be anti-log transformed to obtain the geometric means and their 90% CIs for the

quantities of interest. In addition, 95% confidence intervals (CI) for the mean pharmacokinetic parameters will also be presented.

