6.4.5 Determination of sample size

For AUC, using the equivalence margin of 30% (0.7 to 1.43), an expected ratio of 1, and 90% power to conclude equivalence, the sample size for each group is 27. Approximately 30 volunteers will be recruited to each ethnic group.

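### Section 6.4.3 confines all PK analyses to three-period completers and so drops valid one- and two-period profiles, while the synopsis ties the target of 27 to a different definition of evaluable

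*Protocol*

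**What the plan says.** Section 6.4.3 of the protocol: "Statistical analyses for pharmacokinetic parameters will be performed on the evaluable population". A volunteer is evaluable who "satisfied the inclusion and exclusion criteria, completed the study, and had no major protocol deviation or violation". No other PK set is named.

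The synopsis, in the paragraph on the number of subjects, defines evaluable as "a volunteer completing all study procedures from the screening period to the final blood sampling of the final crossover period". It mentions neither eligibility nor deviations, and it is the text that carries the target of at least 27 evaluable per ethnic group.

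Section 6.4.4 on the three exposure measures, after taking logs: they "will be analyzed using a mixed model with the fixed effect of ethnicity, sequence, treatment, and period and random effect subject".

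Section 6.4.5 gives 27 per group, "using the equivalence margin of 30% (0.7 to 1.43), an expected ratio of 1, and 90% power to conclude equivalence", with about 30 recruited per group.

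Section 3.3.5.3: volunteers who are ineligible or wrongly randomized, or who later fail the criteria, are discontinued; they "will be included for the safety analysis, but will not be included as evaluable volunteers in the analysis of the study". Section 3.4.4 adds that "volunteers will be discontinued if use of prescription medication has occurred during any restricted timeframe", and those timeframes include the washouts. Section 3.3.5.1 also allows withdrawal by the volunteer, on safety grounds, or through loss to follow-up.

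**The concern.** Neither primary quantity needs all three periods. The per-statin ethnic ratio (section 2.1) needs one period on that statin. Each ratio of ratios (section 6.4.2) involves two statins. A Sequence 1 volunteer who withdraws before the third period has complete rosuvastatin and atorvastatin profiles, yet is removed even from the contrast between those two drugs. The exclusion also works by volunteer, so a major deviation confined to the last period removes two clean earlier ones. A random-subject mixed model can take volunteers with one or two periods, but the analysis set removes them first.

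The second issue is which people count as evaluable. Recruitment is steered by one definition and the analysis by another. The site could report 27 evaluable in a group while fewer than 27 enter the analysis on which the power statement rests.

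**Working it through.** **Definitions side by side**

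| Volunteer | Evaluable, synopsis | Evaluable, 6.4.3 |
|---|---|---|
| Completer with a major deviation that did not cause discontinuation | yes | no |
| Completer who missed a procedure, not a major deviation | no, read literally | yes |
| Ineligible or wrongly randomized (discontinued, 3.3.5.3) | no | no |
| Left after one or two periods | no | no |

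The two texts disagree only in the first two rows.

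**The plan's own figure.** The limits are 0.7 to 1.43, so θ = ln(1/0.7) = 0.3567. The expected ratio is 1. The 90% CI implies two one-sided 5% tests. No SD or CV is stated, so 27 cannot be reproduced forwards. Solving backwards, with SE = √2·σw·√(2/n) = 2σw/√n and power ≈ 2Φ(θ/SE − 1.645) − 1, 27 per group gives 90% power at σw = 0.282 (normal) or 0.278 (t, 52 df). I use σw = 0.28 as an assumption:

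- SE = 0.56/√27 = 0.1078
- power = 2Φ(3.31 − 1.645) − 1 = 90.4% (normal); 89.5% (t)

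The result depends on this value. A within-subject CV of 20% would need 15 per group, 25% needs 22, 30% needs 31, 35% needs 41 and 40% needs 52.

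**Effect of keeping incomplete volunteers.** The between-subject SD is also assumed: σb = 0.35. Put S = σw² = 0.0784 and B = σb² = 0.1225, with losses spread evenly over the three sequences and equal in each ethnic group. An ethnicity-by-treatment term is taken as present, since a ratio of ratios cannot be estimated without one. With n3, n2 and n1 volunteers giving three, two and one periods, and ρ = B/(S + 2B) = 0.1225/0.3234 = 0.379, generalised least squares gives for a between-statin contrast:

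effective n = n3 + n2·(2 − ρ)/3 + n1·S/[3(S + B)] = n3 + 0.540·n2 + 0.130·n1

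The variance of one statin's mean in one group is (2/3)/a + (1/3)/c, where a = (effective n)/S and c = n3/(S + 3B) + (2/3)·n2/(S + 2B) + (1/3)·n1/(S + B). Example for three leaving after period 2:

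- a = 28.62/0.0784 = 365.1
- c = 27/0.4459 + 2/0.3234 = 66.7
- variance = 0.00182 + 0.00500 = 0.00682, against 0.2009/27 = 0.00744 for completers only
- SE ratio = √(0.00682/0.00744) = 0.957

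| Loss per group | Leaving | Effective n | SE, ratio of ratios | SE, ethnic ratio |
|---|---|---|---|---|
| 3 of 30 | after period 1 | 27 + 3(0.130) = 27.4 | 0.7% smaller | 3.0% smaller |
| 3 of 30 | after period 2 | 27 + 3(0.540) = 28.6 | 2.9% smaller | 4.3% smaller |
| 6 of 30 | after period 1 | 24 + 6(0.130) = 24.8 | 1.6% smaller | 6.4% smaller |
| 6 of 30 | after period 2 | 24 + 6(0.540) = 27.2 | 6.1% smaller | 8.9% smaller |

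The 10% rows follow from the planned 30 recruited for 27. The 20% rows are illustrative; the protocol gives no such rate.

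Power per ratio of ratios at 20% loss (t; normal) is 84.7%; 86.0% on 24 completers, 86.1%; 87.3% at effective n 24.8, and 89.8%; 90.6% at 27.2. Rounded, that is 85% rising to between 86.5% and 90%.

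**Sensitivity.** The same formula with σb from 0.3 to 0.5 gives an effective n of 27.2–28.7 at 10% loss and 24.5–27.3 at 20%. A fuller model with period and sequence effects (σw 0.278, σb 0.3–0.5) gives completers-only SEs for the ratio of ratios that are 0.4–3% larger at 10% loss. With six per group leaving after period 2 they are 6–7% larger. In that last case 36 of 252 observed profiles are thrown away.

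**The case against.** The planned loss is already paid for. The study recruits 30 to obtain 27, and 27 is the number given for 90% power, so that power is met on completers alone. Completer sets are common in crossover PK work. This stands: a reader might infer that the study is underpowered because of section 6.4.3, and the protocol does not support that.

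The gain also depends on when people leave. If all leave after period 1, the ratios of ratios gain almost nothing (27.4 against 27). A two-period volunteer directly informs one of the section 6.4.2 ratios in Sequences 1 and 3; in Sequence 2 the pair is atorvastatin and simvastatin, which is none of the four. This stands, and the ranges above include it.

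The random subject effect is needed for within-subject correlation in any crossover, and it still serves completers who lack an AUC for one drug. So the analysis set does not make the mixed model pointless; it only withholds part of the data.

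The clash of definitions is narrow, because ineligible volunteers and those discontinued early fail both. What counts as a major deviation may properly be left to the SAP. But the protocol itself gives one term two meanings.

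A reader might also infer that completers are a biased sample. The documents give no direction, mechanism or size for a link between completion and exposure or ethnicity. It remains a possibility, and the remedy carries its own assumption of missingness at random.

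**Conclusion.** The point holds as a modest loss of efficiency together with a narrow inconsistency in definition. At the planned 10% loss the completer restriction costs about 1–3% in the SE of a ratio of ratios and 3–4% in the SE of an ethnic ratio. At 20% it costs about 2–6% and 6–9%. These sizes rest on two SDs that the protocol does not state, on losses balanced over sequences and groups, and on missingness at random. The mismatch between the synopsis and section 6.4.3 needs no assumption; it matters mainly for completers with a major deviation or a missed procedure. The change is worth making because it is cheap and uses samples already taken, but the trial does not fail without it.

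**What to change.** In section 6.4.3:

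- Include in the mixed model every eligible, correctly randomized volunteer with at least one period giving a valid Cmax or AUC.
- Keep eligibility failures out at volunteer level, as section 3.3.5.3 requires. A volunteer later found not to meet the parental-race criterion, for example, must not re-enter an ethnic comparison.
- Apply other deviation-based exclusions only to the affected periods, decided before concentrations are seen.
- Keep the three-period completer set as a sensitivity analysis.
- Use one definition of evaluable in the synopsis and in 6.4.3, and tie the target of 27 to it.

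One boundary needs a sentence. Section 3.3.5.3 also covers volunteers who fail a criterion only after enrollment, and section 3.4.4 calls prescription use an exclusion criterion. The text should say whether periods completed before such an event stay in the analysis. This concerns data already collected; the discontinuation rules are untouched.

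Cost: wording in the protocol and SAP, with no extra volunteers or samples. The downsides are slightly unbalanced data and reliance on missingness at random, which the completer sensitivity analysis helps to probe.

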6.4.4 Methods of statistical analyses

All demographic and baseline data, including medications, will be listed and summarized using standard summary statistics for continuous variables and frequency counts and percentages for categorical variables.

Pharmacokinetic data, C_{\max} , $AUC_{(0-t)}$, and AUC, $t_{1/2z}$, λ_z and CL/F, of each study medication will be summarized for each ethnic group using descriptive statistics, including geometric means and coefficient of variation, and listed. In addition, 95% confidence intervals (CI) for the mean pharmacokinetic parameters will also be presented. Time to peak plasma concentration, t_{\max} , will be summarized using the median value and range for each ethnic group.

Log-transformed C_{\max} , $AUC_{(0-t)}$, and AUC will be analyzed using a mixed model with the fixed effect of ethnicity, sequence, treatment, and period and random effect subject. Appropriate contrasts and their 90% CIs will be produced from the model, these estimates will then be anti-log transformed to obtain the geometric means and their 90% CIs for the

quantities of interest. In addition, 95% confidence intervals (CI) for the mean pharmacokinetic parameters will also be presented.

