Log-transformed C_{max} , $AUC_{(0-t)}$, and AUC will be analyzed using a mixed model with the fixed effect of ethnicity, sequence, treatment, and period and random effect subject. Appropriate contrasts and their 90% CIs will be produced from the model. These estimates will then be anti-log transformed to obtain the geometric means and their 90% CIs for the quantities of interest. In addition, 95% confidence intervals (CI) for the mean pharmacokinetic parameters will also be presented.

Genetic data will not be included in the statistical analyses. Genetic data will be recorded and reported separately.

Clinical Pharmacology Study Protocol
Drug Substance Rosuvastatin calcium
Study Code D3560C00004
Date

Safety data will be summarized and listed by study medications and ethnic groups.

	PAGE
TITLE PAGE	1
PROTOCOL SYNOPSIS	3
TABLE OF CONTENTS	7
LIST OF ABBREVIATIONS AND DEFINITION OF TERMS	11
1. INTRODUCTION	14
1.1 Background	15
1.1.1 Clinical pharmacology of rosuvastatin	15
1.1.2 Clinical pharmacology of atorvastatin	16
1.1.3 Clinical pharmacology of simvastatin	16
1.1.4 Safety of rosuvastatin	16
1.1.5 Safety of atorvastatin	16
1.1.6 Safety of simvastatin	16
1.2 Rationale	16
2. STUDY OBJECTIVES	17
2.1 Primary objective	17
2.2 Secondary objective(s)	17
3. STUDY PLAN AND PROCEDURES	17
3.1 Overall study design	17
3.2 Rationale and risk/benefit assessment	23
3.2.1 Rationale for study design, doses and control groups	23
3.2.2 Risk/benefit and ethical assessment	23
3.3 Selection of study population	23
3.3.1 Study selection record	23
3.3.2 Inclusion criteria	23
3.3.3 Exclusion criteria	24
3.3.4 Restrictions	25
3.3.5 Discontinuation of volunteers from treatment or assessment	25
3.3.5.1 Criteria for discontinuation	25
3.3.5.2 Procedures for discontinuation	26
3.3.5.3 Procedures for handling incorrectly enrolled volunteers	26
3.3.5.4 Procedures for discontinuation from genetic aspects of the study	26
3.4 Treatment(s)	27
3.4.1 Investigational product(s)	27
3.4.1.1 Labeling	27
3.4.1.2 Storage	28
3.4.1.3 Accountability	28

3.4.2	Doses and treatment regimens	28
3.4.3	Method of assigning volunteers to treatment groups	28
3.4.4	Concomitant medication	28
3.4.5	Treatment compliance.....	29
4.	MEASUREMENT OF STUDY VARIABLES	29
4.1	Medical examination and demographic measurements	29
4.1.1	Enrollment medical examination and demographic measurements.....	29
4.1.1.1	Demographics	30
4.1.1.2	Medical History and Complete Physical Exam	30
4.1.1.3	HIV and hepatitis testing	31

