1.2 Rationale

Previous studies have demonstrated that for the same dose of rosuvastatin calcium, systemic exposure in Asian volunteers living in Japan, and of varying Asian ethnic origin living in Singapore and the United States is approximately two-fold higher than the exposure observed in Caucasian volunteers.

The purpose of this trial is to determine whether the pattern of differential pharmacokinetics of rosuvastatin in Japanese and Chinese volunteers versus Caucasian volunteers holds true for atorvastatin calcium and simvastatin as well.

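### The stated mixed model has no ethnicity-by-treatment term, so every ratio of ratios (the primary test statistic) is fixed at exactly 1

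*Protocol*

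**What the plan says.** Section 6.4.2 of the protocol sets the hypothesis: "The primary question is whether the magnitude of the ethnic effect (Chinese or Japanese vs Caucasian) is equivalent" when atorvastatin, or simvastatin, is set against rosuvastatin. It continues: "The test statistics are the ratios of the primary parameter ratios". Four are written out for AUC: Chinese/Caucasian and Japanese/Caucasian, each for atorvastatin and for simvastatin, divided by the same ethnic ratio for rosuvastatin. The same ratios are to be examined for Cmax and AUC(0-t).

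Section 6.4.4 says the log-transformed parameters are analysed "using a mixed model with the fixed effect of ethnicity, sequence, treatment, and period and random effect subject". The synopsis, under Statistical methods, gives the same list: "mixed model with the fixed effect of ethnicity, sequence, treatment, and period and random effect subject". Section 6.4.4 then says: "Appropriate contrasts and their 90% CIs will be produced from the model". Neither place names an interaction, drug-specific ethnic effects or a separate model for each statin.

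The primary objective (section 2.1) is to compare the exposure of each statin in Chinese and Japanese volunteers with that in Caucasian volunteers. Section 1.2 gives the purpose as finding out whether the rosuvastatin pattern "holds true for atorvastatin calcium and simvastatin as well".

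**The concern.** The trial asks whether the ethnic effect depends on the drug. A model with additive ethnicity and treatment effects assumes that it does not. The primary contrast is then a constant and not an estimate, and the 90% CI has no width. Set against the margin of 0.7 to 1.43 in section 6.4.5, such a result meets equivalence for any data. The model also returns one Chinese/Caucasian ratio and one Japanese/Caucasian ratio, each shared by all three statins, so it gives no model-based ethnic ratio per statin for the primary objective either.

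**Working it through.** **Inputs.** Model terms from section 6.4.4 and the synopsis; the four contrasts from section 6.4.2; the margin 0.7 to 1.43 and 27 per ethnic group from section 6.4.5; three sequences (section 3.1), randomised within ethnic group (section 3.4.3). Section 1.2 reports that rosuvastatin exposure in Asian volunteers "is approximately two-fold higher than the exposure observed in Caucasian volunteers". The ethnic ratios for the other statins and all SDs below are assumptions, because the protocol gives none.

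**Step 1: the plan's own figure.** The 27 per group cannot be reproduced, because section 6.4.5 states no SD or CV. It can be back-solved, assuming two one-sided 5% tests and a true ratio of 1: SE = ln(1.43)/(1.645 + 1.645) = 0.3577/3.290 = 0.1087. For a ratio of ratios SE² = 4σ²/n, so σ = 0.1087 × √(27/4) = 0.282, a within-subject CV of about 29%. The conclusion does not depend on this figure, but it shows that the sample size presupposes a contrast with positive variance.

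**Step 2: the contrast under the stated model.** Averaged over sequence and period, the mean log exposure for ethnic group e on drug t is

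m(e,t) = c + E(e) + T(t).

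The ethnic log ratio on any drug is m(Asian,t) − m(Caucasian,t) = E(Asian) − E(Caucasian), which does not involve t. The log ratio of ratios is therefore

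[E(Asian) − E(Caucasian)] − [E(Asian) − E(Caucasian)] = 0.

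Every coefficient of the contrast vector is zero, so the estimate is exp(0) = 1 and its variance is 0.

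**Step 3: the contrast with the interaction.** Now m(e,t) = c + E(e) + T(t) + ET(e,t). For atorvastatin the log ratio of ratios is ET(Asian,A) − ET(Caucasian,A) − ET(Asian,R) + ET(Caucasian,R). Subject effects cancel within person, and the variance is 4σ²/n.

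**Step 4: what the stated model reports.** With complete balanced data, its common ethnic ratio estimates the geometric mean of the three drug-specific ratios.

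| Assumed Asian/Caucasian ratio (rosuva, atorva, simva) | Common ratio from stated model | Ratio of ratios from stated model | True ratios of ratios (atorva, simva) |
|---|---|---|---|
| 2, 2, 2 | (8)^(1/3) = 2.00 | 1.00 | 1.00, 1.00 |
| 2, 1.3, 1 | (2.6)^(1/3) = 1.38 | 1.00 | 0.65, 0.50 |
| 2, 1, 1 | (2)^(1/3) = 1.26 | 1.00 | 0.50, 0.50 |

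The model is right only in the first row, where the pattern carries over in full.

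**Step 5: a fitted example.** One data set was simulated with the protocol's sequences, 27 per group, ratios 2, 1, 1, within-subject log SD 0.285 and between-subject log SD 0.4.

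- Stated model: Chinese/Caucasian 1.327 and Japanese/Caucasian 1.108 on every drug; all four ratios of ratios 1.000, SE 0, 90% CI 1.000 to 1.000.
- With ethnicity-by-treatment added, ratios of ratios (90% CI), SE 0.102:
  - Chinese: atorvastatin 0.54 (0.45 to 0.64), simvastatin 0.53 (0.45 to 0.62)
  - Japanese: atorvastatin 0.52 (0.44 to 0.62), simvastatin 0.52 (0.44 to 0.61)

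All four intervals lie wholly below 0.7, as they should with a true value of 0.5. As a check on step 4, the drug-specific Chinese ratios from the interaction model were 2.022, 1.085 and 1.065, and (2.022 × 1.085 × 1.065)^(1/3) = 1.327, the common ratio from the stated model. The Japanese common ratio follows in the same way: (1.709 × 0.896 × 0.887)^(1/3) = 1.108. This is a single draw and serves only as illustration.

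**The case against.** The best defence is that section 6.4.4 names factors and does not give a full model statement. Section 6.4.2 writes out the quantities wanted, the phrase about appropriate contrasts points to them, and section 6.4.1 promises a comprehensive SAP before database lock. That SAP was not available here and may contain the term. A statistician who ran the contrast would also see at once that it has no variance, so a false claim of equivalence is unlikely to be published unnoticed.

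Some of this stands. The likelier harm is a late change to the primary model in an open-label trial. The descriptive summaries in section 6.4.4 will also show geometric means by drug and ethnic group, so the per-drug pattern will be visible. The direction of the error in the common ratio depends on which drug has the largest ethnic effect; it understates rosuvastatin only if the rosuvastatin ratio exceeds the average.

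The defence does not remove the fault. The protocol did not leave the model open: it gives the same explicit list of effects twice and says the contrasts come from that model. No contrast among main effects yields an interaction. Treatment is itself a model term, so separate models per statin cannot have been meant. The descriptive summaries provide neither the ratios of ratios nor their 90% CIs.

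**Conclusion.** The concern holds. As written, the primary analysis cannot estimate the primary test statistics: all four ratios of ratios, for each exposure parameter, equal 1 with zero standard error. Nor can it give model-based ethnic ratios by drug. The result is algebraic and does not depend on variance, sample size, missing data or the sequence and period terms. Only the illustrations depend on assumed ethnic ratios and SDs: there, true ratios of ratios of 0.50 to 0.65, outside the margin, would be returned as 1.00. Sections 6.4.2 and 6.4.4 contradict each other, and this must be corrected before the model is used.

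**What to change.** In section 6.4.4 and in the synopsis, list the fixed effects as ethnicity, treatment, ethnicity-by-treatment, sequence and period, with subject random. State that the four ratios of ratios in section 6.4.2 are the interaction contrasts of this model. State also that the six per-drug ratios (Chinese/Caucasian and Japanese/Caucasian for each of three statins) are its simple-effect contrasts, each back-transformed with a 90% CI. Check that the SAP carries the same terms.

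The design supports the term, because all three sequences are randomised within each ethnic group and every evaluable volunteer receives all three drugs. It uses (3 − 1) × (3 − 1) = 4 degrees of freedom. With 81 evaluable volunteers and 243 observations, the within-subject residual falls from 243 − 81 − 2 − 2 = 158 to 154. No extra volunteers, samples or visits are needed.
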